- Clinical impact on service users, including new problems identified (number and nature) and problems addressed (number and nature). [Time Frame: 16 months from the start of the study]
- Number of patients with a change in signs and symptoms related to adverse effects of prescribed medicines. Care quality/ clinical gain/ benefit to patients as recorded in notes and on the Profile by the number and nature of all health problems addressed, particularly serious adverse events. [Time Frame: 16 months from the start of the study]
- Prescription changes (number of patients with changes in prescription regimens: drug or dose. Number and nature of changes). [Time Frame: 16 months from the start of the study]

Phase 3

- Description of stakeholder views on ADRe Profile implementation effectiveness (survey rating of the ADRe Profile - Likert scale). A brief survey will be distributed to the main stakeholders (patients, nurses, GP's and pharmacists) following completion of Randomised Controlled Trial. [Time Frame: 22 months from the start of the study]
- Description of stakeholder views on ADRe Profile implementation feasibility (eliciting interview themes). Semi-structured interview with the main stakeholders (patients, nurses, GP's and pharmacists) to explore their views on feasibility of ADRe Profile integration in GP practices. [Time Frame: 22 months from the start of the study].

Secondary Endpoint

- Calculation of the average nurses', GP's and pharmacists' length of time per one ADRe Profile completion. Average length of the health professionals' time involvement with one ADRe Profile. [Time Frame: 16 months from the start of the study]. Phase 2
- Calculation of the cost of nurses', GP's and pharmacists' time, based on average national salary cost per hour. Estimated costs of ADRe implementation in GP practices. [Time Frame: 16 months from the start of the study] Phase 2

- Description of the main stakeholders' views on multidisciplinary collaboration (eliciting interview themes). Semi-structured interview with the main stakeholders (patients, nurses, GP's and pharmacists) to explore their views on whether and how ADRe Profile contributed to multidisciplinary collaboration between nurses, doctors and pharmacists. [Time Frame: 22 months from the start of the study] Phase 3

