7.1 Primary Endpoint Efficacy Analysis

Differences between before and after the intervention will be calculated for: problems addressed, prescription regimens, NHS use, and compared, adjusting for site. The impact of age, diagnoses, and medicines' use (numbers and types of medicines prescribed) will be accounted.

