7.4 Sample Size

RCT (sample = 60): Previously, in a 'before and after' single arm intervention study, with participants acting as their own controls, 17/19 (89%) had improvement in at least 1 clinical problem when ADRe Profiles for polypharmacy were used (Jordan et

SU Non CTIMP Healthcare Research Protocol
al submitted). We hypothesised that 9/19 (47%) would have shown some improvement without intervention, necessitating an effective sample of 40 patients (20 in each arm), with 5% significance and 90% power (Uitenbroek 1997). Based on the reported intra-cluster coefficient (0.02), (Jordan et al 2015), and a design effect of 1.18, to achieve an effective sample size of 40, we need an actual sample size of 48 (Killip et al 2004). 10 patients in each of 6 clusters (GP practices) allows for 20% loss to follow up, which is realistic in general practice, where either patient or nurse may be unavailable for follow up.

For the survey, all health professionals involved with the intervention arm (n=9) and all service users in the intervention arm (n=30) will be included. The aim is to gain stakeholder views on the intervention.

For the qualitative interviews, a convenience sample of 12 participants will be selected. This will include all nurses, GP's and pharmacists in the intervention arm, as well as a purposive sample of 3 patients. The patients will be selected based on the most positive and most negative responses in the survey. The aim is to gain stakeholder views on the intervention and to supplement and illustrate the RCT data.

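### No single primary RCT endpoint: section 2.1 makes three overlapping outcomes primary without ranking, section 7.1 analyses a different set, and section 7.4 sizes the trial on one binary outcome at 5%

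*Combined protocol and SAP*

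**What the plan says.** **Section 2.1.** Eleven bullets stand under Primary Endpoint: six for Phase 1, three for Phase 2 (the RCT) and two for Phase 3. The three RCT bullets are not ranked:

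1. "Clinical impact on service users, including new problems identified (number and nature) and problems addressed (number and nature").
2. The number of patients whose signs and symptoms related to adverse effects change. This too is recorded through the health problems addressed.
3. "Prescription changes (number of patients with changes in prescription regimens: drug or dose. Number and nature of changes").

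**Section 7.1.** Under its heading for the primary efficacy analysis, the plan states: "Differences between before and after the intervention will be calculated for: problems addressed, prescription regimens, NHS use, and compared, adjusting for site". NHS use is not an endpoint in section 2.1, and the signs-and-symptoms endpoint is not named here.

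**Section 7.2 (Secondary Endpoint Efficacy Analysis).** Marked not applicable.

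**Section 7.4 (repeated in 3.1).** The RCT is sized on a single binary outcome. In an earlier single-arm study "17/19 (89%) had improvement in at least 1 clinical problem when ADRe Profiles for polypharmacy were used"; for the comparison, "We hypothesised that 9/19 (47%) would have shown some improvement without intervention". The calculation is done "with 5% significance and 90% power".

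No section gives a testing order, a division of the 5%, a rule for co-primary endpoints or any other multiplicity adjustment. None defines what result would count as success.

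**The concern.** The sample size treats the RCT as a test of one hypothesis at 5%. The endpoint list and the primary analysis do not. They name several outcomes as primary, they disagree on which ones, and neither states the sized outcome in the terms used for sizing. Section 7.2 is empty, so there is no lower tier for the rest.

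At the end of the trial, any of these outcomes could be presented as the primary result. If the one that reached significance were chosen, the 5% in section 7.4 would not describe the error rate of the conclusion, and the 90% power would belong to an outcome other than the one reported. Several bullets also bundle measures: new problems with problems addressed, and patients with a prescription change with the number of changes. This leaves further choice within each bullet.

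**Working it through.** **1. The plan's own figure**

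Inputs (section 7.4): p1 = 17/19 = 0.895; p2 = 9/19 = 0.474; significance 5%, sidedness not stated; power 90%; intra-cluster coefficient 0.02; 10 patients in each of 6 practices; 20% loss.

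Pooled formula per arm: n = [z_a √(2p̄(1−p̄)) + z_b √(p1(1−p1) + p2(1−p2))]² / (p1 − p2)², with p̄ = 26/38 = 0.684.

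- √(2 × 0.684 × 0.316) = 0.657; √(0.094 + 0.249) = 0.586; (p1 − p2)² = 0.421² = 0.177.
- One-sided 5%: (1.645 × 0.657 + 1.282 × 0.586)² / 0.177 = 18.9, so 19 per arm (20 with the rounded rates 0.89 and 0.47).
- Two-sided 5%: (1.960 × 0.657 + 1.282 × 0.586)² / 0.177 = 23.5, so 24 per arm (29 with continuity correction).
- Two-sided, unpooled variance: (1.960 + 1.282)² × 0.343 / 0.177 = 20.4, so 21 per arm.

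The stated 20 per arm is therefore reproduced by a one-sided pooled calculation, and within one patient per arm by a two-sided unpooled one. With 20 per arm, power by the pooled formula is about 91% one-sided and 84% two-sided.

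Design effect: 1 + (10 − 1) × 0.02 = 1.18. Then 40 × 1.18 = 47.2, taken as 48, and 48 / 0.8 = 60. The plan's chain of 40, 48 and 60 reproduces. It covers one outcome and one test.

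**2. The outcome sets side by side**

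| Outcome | Primary in 2.1 | In 7.1 | Used for sizing in 7.4 |
|---|---|---|---|
| New problems identified | yes | not named | no |
| Problems addressed | yes | yes | no |
| Change in signs and symptoms | yes | not named | no (nearest in meaning) |
| Prescription changes | yes | yes | no |
| NHS use | no | yes | no |
| Improvement in at least one clinical problem | not in those terms | not named | yes |

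**3. Error rate if any one significant result were reported as the primary result**

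Assumptions: each outcome is tested two-sided at 5%, the intervention affects none of them, and one success suffices. For k independent tests the chance of at least one false positive is 1 − 0.95^k:

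- k = 3 (the bullets in 2.1): 1 − 0.95³ = 14.3%.
- k = 4 (those three plus NHS use): 1 − 0.95⁴ = 18.5%.

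For equally correlated normal test statistics, 1,000,000 simulated draws give:

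| Assumed pairwise correlation | k = 3 | k = 4 |
|---|---|---|
| 0.3 | 13.5% | 17.4% |
| 0.5 | 12.5% | 15.6% |
| 0.7 | 10.9% | 13.1% |
| 0.9 | 8.4% | 9.4% |

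The documents give no correlations; these are assumed values that show a range.

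**4. Cost of sharing the 5% instead of naming one primary**

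With 20 per arm effective, two-sided power on the sized outcome falls to about 70% at 0.05/3 = 0.0167 and about 66% at 0.05/4 = 0.0125.

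**The case against.** The strongest reply is that the plan never says one significant endpoint would show that ADRe works. The matching primary objective is worded as exploration, section 7.5 calls the regressions exploratory, and the only test it names for the RCT is McNemar's, on before and after profiles. No between-arm test is named for any of these outcomes. This stands: the error rates belong to an assumed way of reporting. It does not remove the point, because the trial is justified by a two-arm calculation at 5% and 90% power and has a section for primary efficacy analysis. If no confirmatory claim is intended, the plan should say so.

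A reader might go further than the documents allow in four ways:

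- **That the error rate is 14-19%.** Those values need independent tests. Problems addressed appear in both the first and second endpoints, so positive correlation is likely, and independence gives the upper end for three or four such tests. In the other direction, the bundled measures and the McNemar comparisons mean that the number of possible tests may exceed four.
- **That the plan lists four primary RCT outcomes.** It does not. Sections 2.1 and 7.1 each name three headings, and four arises only by merging them. The mismatch comes first.
- **That six practices make a chance finding likely.** The number of practices is a matter of clustering, which this calculation does not model.
- **That the repair is free of any power question.** Sidedness is not stated, and a two-sided pooled calculation needs 24 per arm against the stated 20.

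Two practical objections also stand. The sized outcome has to be added to section 2.1, since a change in signs and symptoms is not the same as an improvement. It must also be obtainable in both arms: section 4.5 gives the control arm notes extraction and standard care, without a completed Profile.

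**Conclusion.** The point holds as an inconsistency between the endpoint list, the primary analysis and the sizing, with multiplicity left open. That much rests on the text alone.

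The size of the consequence is conditional. If any one significant outcome were reported as the primary result, the false-positive chance would be above 5%: at most about 14% for three tests or 19% for four, and about 8-13% or 9-16% at correlations of 0.9 to 0.5. This rests on the assumed correlations and on an any-one-suffices reading that the plan neither states nor excludes. The documents do not support the claim that the trial's error rate is 14-19%. The plan should be changed before data are seen; the sample size arithmetic itself is not in dispute here, apart from the unstated sidedness.

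**What to change.** - **Sections 2.1 and 7.1:** name the outcome used in 7.4, a patient with improvement in at least one clinical problem, as the single primary RCT endpoint, compared between arms at the 5% level used for sizing. Define it from data available in both arms, and reconcile the signs-and-symptoms bullet with it.
- **Section 7.4:** state whether the 5% is one- or two-sided. If two-sided, restate the power and the formula used (about 84% with 20 per arm by the pooled formula).
- **Sections 2.1, 7.1 and 7.2:** relabel new problems, problems addressed, prescription changes and NHS use as secondary or exploratory. Report them as estimates with 95% confidence intervals and no stand-alone claim of effect. Section 7.2 should no longer read as not applicable.

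A written testing order would be an alternative, but the bundled outcomes cannot enter one until a single measure is chosen for each. Splitting the 5% would cost the power shown in step 4.

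**Cost:** a text amendment, the work of defining the sized outcome in both arms, and a restated power if the test is two-sided. The downside is that the relabelled outcomes can no longer support a primary claim on their own.

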Data will be entered into excel via the electronic version of ADRe, imported into SPSS and described for the before and after ADRe administrations. Statistical analysis: differences between before and after the intervention will be calculated for: number and nature of problems addressed, prescription regimens, and NHS use. The impact of GP practice, age, diagnoses, and medicines' use (numbers and types of medicines prescribed) will be described and accounted for in exploratory bivariate and multivariate regression analyses. To explore the recorded changes and potential for further clinical gains, putative aetiologies of service users' signs and symptoms will be ascribed, using clinical information from medical and nursing records, including, but not restricted to, information on ADRe, and the list of medications prescribed (and over the counter). The ascription will be checked by supervisors using manufacturers' literature and formularies. Juxtaposition of ADRe and medication lists will generate suggestions for changes to improve the processes and possibly the outcomes of care. The prevalence of problems on the before and after profiles will be compared with two by two contingency tables, using McNemar's test for related dichotomous variables (Altman 1991).

Survey

Data will be described using the Statistical Package for Social Sciences (SPSS) and later combined with the interview results.

Interviews and recorded ADRe consultations

All interviews (and relevant parts of ADRe consultations) will be transcribed verbatim by the researcher/professional transcriber and anonymised. Transcripts will be

SU Non CTIMP Healthcare Research Protocol

coded, categorised, analysed and interpreted alongside the data of all completed cases, to identify, analyse and report patterns within data (Braun and Clark, 2006). The transcripts will be analysed by the team using the constant comparative method which will provide a systematic, re-iterative way of comparing and contrasting emerging codes, categories and concepts and ensure that theoretical perspectives are embedded in the description of change. Two researchers ([name]) will ensure validity of the analysis and verify interpretation. Disagreements will be resolved through discussion at team meetings. Diaries/logs will also be analysed in association with interview transcripts.

Triangulation

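### One Phase 2 primary endpoint is both medicine-related and all-cause, section 7.4 powers a third event with no stated medicine link, and a relatedness judgement could draw on completed Profiles held in one arm only

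*Combined protocol and SAP*

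**What the plan says.** Section 2.1 lists three Phase 2 primary endpoints. The second is written in two sentences. The first counts patients and requires a link to medicines: "Number of patients with a change in signs and symptoms related to adverse effects of prescribed medicines". The second says that benefit is measured "as recorded in notes and on the Profile by the number and nature of all health problems addressed", which counts problems and requires no link.

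Section 7.4 uses another event. The intervention-arm rate comes from an earlier single-arm study in which "17/19 (89%) had improvement in at least 1 clinical problem when ADRe Profiles for polypharmacy were used". For the control arm, "We hypothesised that 9/19 (47%) would have shown some improvement without intervention". The result is given as "necessitating an effective sample of 40 patients (20 in each arm), with 5% significance and 90% power".

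Section 7.5 describes the only attribution step: "putative aetiologies of service users' signs and symptoms will be ascribed, using clinical information from medical and nursing records", with sources "including, but not restricted to, information on ADRe, and the list of medications prescribed". Supervisors check the result. The stated purpose is exploratory. No relatedness criteria and no masking of the step are given.

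Section 4.5 schedules a Profile populated from medical notes in both arms at both RCT steps (Forms 08 and 13 in section 8.3). Self-completed and nurse- or researcher-completed Profiles (Forms 09, 10, 14 and 15) are scheduled in the intervention arm only; the control column shows standard of care in those rows. Section 4.3 keeps researchers unaware of allocation until they have extracted the notes.

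**The concern.** The three descriptions differ in whether a medicine link is needed, in unit (patients or problems) and in direction (any change, or improvement). Nothing says which decides who is an event. Section 7.1 does not settle it: it lists problems addressed, prescription regimens and NHS use.

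Two things follow. First, a power figure holds only for the event whose rates went into it. Improvements that are also medicine-related are at most as frequent as improvements of any kind, so the 90% does not carry over. Second, if the first sentence defines the event, someone must judge relatedness, and the only procedure described may use patient-elicited information that the control arm does not have. A completed Profile also reveals the arm to whoever makes the judgement. With the choice left open, it could be made after the data are seen.

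**Working it through.** **Inputs from section 7.4.** Rates 17/19 = 0.895 and 9/19 = 0.474; 5% significance (sidedness not stated); 90% power; 20 effective patients per arm; ICC 0.02; 6 practices of 10; 20% loss.

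**Reproducing the plan's figure.** Two-sided, unpooled variance:

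n per arm = (1.960 + 1.282)² × [0.895×0.105 + 0.474×0.526] / (0.895 − 0.474)² = 10.51 × (0.0942 + 0.2493) / 0.1773 = 20.4.

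That is 21 per arm when rounded up, against the stated 20. The design effect is 1 + 9×0.02 = 1.18; 40 × 1.18 = 47.2, so 48; 48 / 0.8 = 60. The chain reproduces closely, so the arithmetic is not at issue. What matters is the event it applies to.

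**Power if relatedness is required.** Let q be the share of improved patients whose improvement is labelled medicine-related. The documents give no value, so q is assumed, and here it is equal in both arms. The rates become q×17/19 and q×9/19. With n = 20 per arm, SE = √{[p₁(1−p₁) + p₂(1−p₂)]/20} and power = Φ[(p₁−p₂)/SE − 1.96].

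| q (assumed) | p₁ | p₂ | Difference | SE | Power, unpooled | Power, pooled |
|---|---|---|---|---|---|---|
| 1.0 | 0.895 | 0.474 | 0.421 | 0.131 | 0.895 | 0.845 |
| 0.9 | 0.805 | 0.426 | 0.379 | 0.142 | 0.763 | 0.708 |
| 0.8 | 0.716 | 0.379 | 0.337 | 0.148 | 0.623 | 0.576 |
| 0.7 | 0.626 | 0.332 | 0.295 | 0.151 | 0.497 | 0.461 |
| 0.5 | 0.447 | 0.237 | 0.211 | 0.146 | 0.301 | 0.284 |

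The pooled column uses the pooled variance under the null. The pattern does not depend on the formula.

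**Unequal labelling with no true effect.** Let 0.474 improve in both arms, with assumed labelling shares that differ by arm, and take an unadjusted two-sided z test with 20 per arm.

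- Shares 0.9 and 0.7: rates 0.426 and 0.332, a spurious difference of 0.095 with SE 0.153, and a rejection probability of 0.095.
- Shares 0.9 and 0.6: rates 0.426 and 0.284, a spurious difference of 0.142 with SE 0.150, and a rejection probability of 0.158.

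The nominal level is 0.05. These cases show how the mechanism works. They are not estimates for this trial, and the plan does not name this test.

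**The case against.** The strongest reply is that the plan never makes attribution the rule for events. Section 7.5 introduces it to explore recorded changes, and under the second sentence of the endpoint, or the event in 7.4, no attribution is needed. This stands: a reader might infer that event status depends on the 7.5 step, but that follows only if the first sentence governs. It does not remove the problem, because the first sentence is a declared primary endpoint and would otherwise have no rule at all.

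A reader might also infer that the control arm has no ADRe information. Section 4.5 does not support that. Both arms have a notes-populated Profile at both steps, and records and medication lists are further sources. The asymmetry is confined to self-completed and nurse- or researcher-completed Profiles.

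The medicine link could also be read as describing the Profile's item set, since section 4.9 presents the tool as collecting possible adverse effects. That reading brings the endpoint closer to 7.4, but the plan does not state it.

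On size, every q is assumed, and low values may be pessimistic because one related problem is enough. Section 1.3 reports a mean of 4.9 problems ameliorated (SD 3.6, range 1 to 11) in one care-home study. Suppose that pattern held, each problem was independently medicine-related with assumed probability 0.5, and problems beyond the first were negative binomial with mean 3.9 and SD 3.6. Then k = 3.9²/(3.6² − 3.9) = 1.68 and q = 1 − 0.5×(1 + 0.5×3.9/1.68)^(−1.68) = 0.86. That lies between the 0.8 and 0.9 rows, where power is 0.62 to 0.76. It is still below 90%, and it speaks only to patients who had the Profile.

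Finally, more information can rule out a medicine cause as well as suggest one, so the direction of any labelling difference is not established.

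**Conclusion.** The point holds as a defect of definition with consequences for power and ascertainment. The endpoint does not say whether relatedness is required or who judges it, and the 90% power applies only to improvement in at least 1 clinical problem. If relatedness is added equally in both arms, power is lower, illustratively 0.76 to 0.30 for assumed shares of 0.9 to 0.5. If the first sentence governs, labelling can differ between arms with no difference in patients.

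The documents do not support the stronger conclusions that the trial is underpowered for the event it was sized on, or that its false-positive rate is 9.5% or 16%. The first fails because 7.4 reproduces closely; the second because those figures rest on assumed shares and on an unadjusted test that the plan does not name (7.1 adjusts for site; 7.5 names McNemar's test and exploratory regression).

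**What to change.** 1. In sections 2.1 and 7.4, name improvement in at least 1 problem as the event for the between-arm comparison, and say that the 90% power refers to it.
2. Ascertain that event in both arms from the notes-populated Profiles only (Forms 08 and 13), and not from Forms 09, 10, 14 or 15. Referring to the baseline record in general would not be enough, because in the intervention arm it includes Forms 09 and 10.
3. Keep medicine-related change as a separately reported outcome, since the primary objective in 2.1 concerns problems that could be attributable to polypharmacy. Make the attribution in both arms from Forms 07 and 08 only, before endpoint data are read and before allocation is known, and state that the 90% power does not apply to it.
4. In section 7.5, separate this attribution from the exploratory one, which may still use every source.

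**Cost.** Rewording of 2.1, 7.4 and 7.5, and earlier attribution work; no new data. Patient-elicited information from the intervention arm is not used in the between-arm comparison, but it can still be described within that arm. Section 7.4 does not say how improvement was recorded in the earlier 19 patients, so it should state as an assumption that the 89% and 47% also hold for notes-based ascertainment.

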1.3 Clinical Data

Medication monitoring and monitoring patients for potential adverse drug reactions has been described as an 'orphan task' in the past due to its position on the interprofessional boundary between pharmacy, medicine and nursing and the subsequent deficiency in ownership (Jordan, 2002, Jordan et al., 2016). Recent studies confirm the lack of clarity of the nurses' roles in medication management (De Baetselier et al., 2019) and effective teamwork has been affirmed as a facilitator of safe management of polypharmacy (WHO, 2019), and medication management overall (WHO, 2017). ADRe Profile is an instrument that involves nurses, pharmacists, prescribers and patients in monitoring for adverse drug reactions to medicines. Nurses and patients identify the problems and may solve some of them, pharmacists review the medicines and prescribers may be provided with recommendations to consider adjustment of the prescriptions.

To date, two randomised controlled trials and five observational/before and after studies have investigated the clinical impact of the ADRe Profile. In total, 168 study participants had the ADRe Profile implemented. Majority of the participants were prescribed mental health medicines (antipsychotics, antidepressants or anti-epileptics), one study included patients with respiratory diseases, taking bronchodilators, corticosteroids or leukotriene receptor antagonists. The setting was mostly in the community, with 3 nursing homes, 3 community mental health settings and one outpatient respiratory clinic.

In two of the community mental health settings, the mean number of problems actioned increased from 0.35 with no ADRe Profile to 3 with ADRe Profile (Jordan et al., 2002; Jordan, 2002). Little change in the number of problems actioned was noted in the comparator groups. The mean number of problems detected increased from 2 without the Profile to 9 with the Profile in one of the studies (Jordan, 2002), no information was offered in the other study. Most actions taken were to alleviate physical health problems.

Another study from an acute mental health service setting identified and addressed health problems for all participants (the mean increase of actions taken was 11.9, SD = 4.7, range 2-20) (Jones et al., 2016). Some of the problems identified were orthostatic hypotension, hypertension, constipation or inadequate diet, two of the

SU Non CTIMP Healthcare Research Protocol

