Service users – ADRe Profile completion: Previous work in the nursing homes and a respiratory clinic indicates that no physical or emotional harms emanate from this intervention, and the physical health of all participants has benefitted (Gabe et al., 2014; Jordan et al., 2015; Jones et al., 2016; Jordan et al., 2019). We do not foresee any risks of physical or emotional harm in this or future studies. We foresee no legal or organisational risk from this study. Any changes to patient management will be based on the professional judgment of staff delivering routine care, and not directed by the study procedures. The intervention only aims to enhance patient monitoring to inform professional judgement. All questions and observations are of a nature that should be pursued under routine care. Time will be required by nurses to complete the ADRe profiles; however, the clinical gains reported in care home studies are likely to outweigh any diversion of resources (Jordan et al., 2015, 2014, 2019). Should any answers in the ADRe Profile raise the nurse-researcher's concern about physical or mental health and well-being of the participant, clinical judgment will be applied and the participant will be advised or referred to their general practitioner. Completed ADRe profiles will be passed to the pharmacist associated with the GP practice and academic pharmacists and thence prescribers.

Balance of risks and benefits of participation in the ADRe Profile completion:

Risk	Benefit

- Breach of confidentiality- Adjustment of medicines, additional prescriptions or de-prescribing- Possible additional health service contacts- Possible misunderstanding (esp. people who have difficulty speaking or understanding English)	
- Additional medication review- Potential identification and amelioration of health and well-being problems- Opportunity to discuss therapeutic regimen with academic clinicians, and access ADRe's supporting information.

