6.1 General Definitions

Adverse Event (AE)

An AE is any untoward medical occurrence in a subject to whom a medicinal product has been administered, including occurrences which are not necessarily caused by or related to that product. An AE can therefore be any unfavourable and unintended sign (including an abnormal laboratory finding), symptom or disease temporarily associated with study activities.

Serious Adverse Event (SAE)

An SAE fulfils at least one of the following criteria:

- Is fatal – results in death (NOTE: death is an outcome, not an event)
- Is life-threatening
- Requires inpatient hospitalisation or prolongation of existing hospitalisation
- Results in persistent or significant disability/incapacity
- Is a congenital anomaly/birth defect
- Is otherwise considered medically significant by the Investigator

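### The Phase 2 benefit count has no baseline condition and draws on a fuller record in the intervention arm, so treated in-trial problems and extra recording can both count as gain

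*Combined protocol and SAP*

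**What the plan says.** Section 2.1 (Primary Endpoint, Phase 2) lists clinical impact, "including new problems identified (number and nature) and problems addressed (number and nature". It then lists care quality, clinical gain or benefit, measured from the notes and the Profile by "the number and nature of all health problems addressed, particularly serious adverse events". It does not say when a problem must have begun, or whether a new problem is one newly found or one newly arisen.

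Section 7.5 carries the count forward: "differences between before and after the intervention will be calculated for: number and nature of problems addressed, prescription regimens, and NHS use". Section 7.1 has a similar list, adjusted for site. Section 7.5 adds: "The prevalence of problems on the before and after profiles will be compared with two by two contingency tables, using McNemar's test".

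Section 7.3 (Safety Endpoints) reads N/A. Section 1.4 names, among the risks of completing the Profile, "Adjustment of medicines, additional prescriptions or de-prescribing".

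The schedule in 4.5 has the notes read in both arms at steps 1 and 2. Self-completed and nurse- or researcher-completed Profiles appear in the intervention arm only; controls have standard of care. In 8.3 the notes-derived records are Form 08 (baseline) and Form 13 (endpoint). Section 4.3 keeps researchers unaware of allocation until they have read the notes.

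**The concern.** Two features of the count can raise it without better care.

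The first is onset. A symptom that starts after a medicine change prompted by the Profile, and is then treated, meets the wording of a problem addressed. The serious-event definition in 6.1 has no onset limit either; one criterion is "Requires inpatient hospitalisation or prolongation of existing hospitalisation". With no safety endpoint, no planned comparison between arms would offset such events. If the problem is still there on the after profile, the McNemar table counts it as a worsening, so one observation adds to benefit in one analysis and to harm in another.

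The second is the size of the record. Benefit is scored from notes and Profile together, and only one arm has Profiles. Symptoms that would have settled anyway are more visible in that arm. At stake is whether a difference in the main Phase 2 benefit measure can be read as better care.

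**Working it through.** **The plan's own figures (3.1 and 7.4).** Inputs: 17/19 = 0.895 against 9/19 = 0.474, 5% significance, 90% power, intra-cluster coefficient 0.02, 10 patients per practice, 20% loss.
- Unpooled two-sided formula: (1.960 + 1.282)² × (0.895×0.105 + 0.474×0.526) / 0.421² = 20.4 per arm, against the stated 20.
- Design effect: 1 + 9 × 0.02 = 1.18. Then 40 × 1.18 = 47.2 (stated as 48), and 48 / 0.8 = 60.

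These reproduce closely enough. They rest on improvement in at least one clinical problem, which already suggests an existing problem, so the point below changes none of them.

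**Onset.** The documents give no rate of new treated problems, so q is an assumption. Suppose ADRe has no effect on baseline problems (0.474 in both arms) and new treated problems occur in a share q of intervention patients only. The share with at least one problem addressed becomes 1 − (1 − 0.474)(1 − q). The last column is the chance that a two-sided pooled test at an effective 20 per arm is significant in favour of ADRe.

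| q | Intervention | Control | Spurious gain | Significant for ADRe |
|---|---|---|---|---|
| 0 | 47.4% | 47.4% | 0 points | 2.1% |
| 0.1 | 52.6% | 47.4% | 5 points | 4.5% |
| 0.2 | 57.9% | 47.4% | 11 points | 8.6% |
| 0.3 | 63.2% | 47.4% | 16 points | 15.5% |

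**McNemar, one item, invented counts.**
- Six baseline problems addressed and resolved, none new: addressed count 6; discordant pairs 6 and 0; exact p = 2 × 0.5⁶ = 0.031.
- Add six new problems, treated but still present on the after profile: addressed count 12; pairs 6 and 6; p = 1.0.
- Let those six instead arise and resolve between profiles: addressed count still 12; pairs 6 and 0; p = 0.031. McNemar does not see them.

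**Size of the record.** Section 1.3 reports, for one community mental health study: "The mean number of problems detected increased from 2 without the Profile to 9 with the Profile". Give every recorded problem the same chance m of improving in both arms, and set m so that 2 problems give the planned control rate: 1 − (1 − m)² = 0.474, so m = 0.275.
- Independent problems: 9 problems give 1 − 0.725⁹ = 94%.
- Correlated problems: use a beta-binomial model with within-patient correlation r, resetting m so that (1 − m)² + r·m(1 − m) = 0.526 and 2 problems still give 47%.

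| r (assumed) | m | 2 problems | 9 problems |
|---|---|---|---|
| 0 | 27.5% | 47% | 94% |
| 0.1 | 28.9% | 47% | 88% |
| 0.2 | 30.4% | 47% | 82% |
| 0.3 | 32.1% | 47% | 77% |

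This models the number of recorded problems. It says nothing about onset.

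**The case against.** The natural reading of the endpoint is milder than its wording allows. Section 2.1 asks whether the Profile identifies problems that could be due to polypharmacy, and 1.3 describes earlier studies finding problems that had gone unattended, two of them potentially life-threatening. On that reading, new means newly detected, and the serious events are existing reactions that the Profile uncovers. A reader might infer that the plan sets out to credit in-trial serious events as benefit. The documents do not support that: the wording permits it without showing that it is intended.

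A reader might also infer that every new problem is a loss in the McNemar table. It is one only if still present on the after profile. Section 7.5 does not make McNemar's test the comparison between arms, and for controls it could use notes-derived items only.

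The plan has partial safeguards. Adverse events are recorded (6.3; Forms 16 and 17 in 8.3), the nature of problems is reported with their number, and 7.5 assigns putative causes to signs and symptoms, checked by supervisors. These make a harm less likely to go unseen. None removes it from the count or compares it between arms.

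Finally, a problem that improves because the Profile found it is the benefit the trial is looking for, and the illustration cannot separate that from better recording. Control notes are also re-read at step 2, so new problems can enter in both arms. All of this stands. It limits the size that can be claimed, but it supplies neither a baseline condition nor an equal record.

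**Conclusion.** The point holds as a gap in the endpoint definition. As written, the benefit count can credit a problem that arose after randomisation and was treated, no safety endpoint offsets it, and the record from which problems are scored is fuller in the intervention arm. Part of any difference between arms can therefore reflect recording.

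The size is not known. The spurious gain of 5 to 16 points assumes new treated problems in 10% to 30% of intervention patients and none in controls. The rise from 47% to 77–94% assumes a move from 2 to 9 recorded problems, taken from one study in a different population, and an equal chance of improvement per problem. A reader might infer from the 94% that recording alone explains the whole planned effect of 47% to 89%. That needs near-independence between problems: at 9 problems, even a correlation of 0.1 falls just short (88%), and 0.3 gives 77%. The figures show that the effect could be material, not that it will occur.

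The sample-size figures are unaffected. This is a cheap improvement.

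**What to change.** In 2.1 and 7.5:

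1. Define new problems identified as problems newly detected at step 1. Report problems with onset after randomisation separately by arm, as new problems or harms and not as benefit. State how a problem still present on the after profile enters the McNemar table.
2. Beside the planned count, report in both arms the share of problems on the baseline notes-derived list (Form 08, completed before allocation is known, as 4.3 provides) that improved. Judge improvement in both arms from the endpoint notes-derived form only (Form 13), and use this measure for the between-arm comparison of improvement. List and measurement then come from the same source in each arm. Onset or improvement reported on a Profile should not enter this comparison, because controls have no Profile.
3. Describe problems detected by the Profile, and their resolution, as intervention-arm results.

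The cost is endpoint wording, one onset field per problem and a somewhat smaller benefit count. Forms 08 and 13 are already planned in both arms. The notes-only measure gives no credit for problems found only by the Profile, which is why it sits beside the planned count. One limit remains: use of the Profile may make intervention-arm notes fuller at step 2, and 4.3 does not say whether the step 2 notes are also read without knowledge of allocation. The report should say so.
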